9.2 Analysis Populations

The following subject populations will be created:

- Intent-to-Treat (ITT) Population: All randomized subjects.
- Safety Population: All subjects who receive at least 1 dose of study drug.
- Modified Intent-to-Treat (mITT) Population: All randomized subjects excluding those who subsequently demonstrate a positive test result for other concomitant vaginal or cervical infections at baseline (e.g. *C trachomatis*, *N. gonorrhoeae*) which may interfere with the efficacy assessment for BV or who have a baseline Nugent score < 4.
- Per Protocol (PP) Population: Includes all subjects who qualify for the mITT population and who follow important components of the trial (including subjects who adhere to treatment and follow-up for efficacy within the prescribed timeframe).

Subjects in the MITT population who discontinue early from the study and do not have an assessment of clinical cure and bacteriological cure will be included in the mITT population analyses as treatment failures. These subjects without outcomes, but are classified as treatment failures will not be included in the PP analyses.

To establish bioequivalence, the 90% confidence interval for the primary endpoint (the difference in the proportion of subjects achieving a clinical cure between metronidazole 0.75% vaginal gel (GDC-229; test product) and metronidazole 0.75% vaginal gel (Oceanside Pharmaceuticals) must be within [0.20, +0.20] for dichotomous variables, using the PP population.

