9.6 Efficacy Analyses

9.6.1 Primary Endpoints

The primary endpoint is the clinical cure at the Test of Cure Visit (Visit 3) and includes the following:

- Resolution of the abnormal vaginal discharge to a normal physiologic discharge
- Negative whiff test
- Presence of clue cells at < 20% of the total epithelial cells on microscopic examination of the saline wet mount

The mITT population will be used to compare both the test and reference products to placebo. The PP population will be used to evaluate bioequivalence between the test and reference products.

To assess adequate study sensitivity the test and references products need to be statistically superior ($p<0.05$, 2-sided) to placebo using the mITT population.

To establish bioequivalence, the 90% confidence interval for the primary endpoint (the difference [test-reference] in clinical cure rate) must be within [-0.20, +0.20], using the PP population.

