2.4 Study Endpoints

2.4.1 Primary Endpoint

The primary study endpoint is “Clinical Cure”, defined as the resolution at the Test of Cure visit of the following three abnormal BV signs included in Amsel’s criteria:

- Return to normal physiological vaginal discharge as determined by the investigator
- Negative whiff test
- The presence of clue cells at <20% of the total epithelial cells on microscopic examination of the saline wet mount.

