3.4 Analysis Populations

All Screened Population: all subjects who signed Consent Form and screened at the study sites.

Intent-to-Treat (ITT) Population: All randomized subjects.

Safety Population: All randomized subjects who received at least 1 dose of study drug. If the drug accountability is unknown (e.g., due to being lost to follow-up after being randomized) then subjects will be assumed to have taken study drug and included in the safety population. Subjects reporting 0 doses will be excluded.

Modified Intent-to-Treat (mITT) Population: a subset of the Safety Population who also met all 4 Amsel's criteria at baseline, but excluding those who subsequently demonstrate a positive or indeterminate test result for other concomitant vaginal or cervical infections at baseline (e.g. *C. trachomatis*, *N. gonorrhoeae*) which may interfere with the efficacy assessment for BV, or who have a baseline Nugent's score < 4. If baseline STI value is missing, use the Post-Treatment Assessment Visit infection test result. Subjects without a Nugent's score at baseline will be excluded from the mITT population.

Per Protocol (PP) Population: All mITT subjects except for those who had at least one of the protocol deviations listed below. If lack of efficacy (LOE) is the discontinuation reason and the subject took at least 3 doses, then the subject will be included in PP as a treatment failure and then the 6 protocol deviations below will not exclude those subjects:

1. Used topical or systemic antimicrobial drugs after randomization, this includes the following drug classes: antimycotics, antibacterials, antiprotozoals, gynecological anti-infectives, antiseptics and antifungals.
2. Used non-study vaginal products during the study
3. Did not start treatment within 2 days of randomization
4. Took less than 5 doses of study drug
5. Test of cure visit (V3) was not in the Study Day 22 – 31 window, i.e., Visit 3 was not 21 – 30 days after randomization
6. Test of cure visit (V3) not done

Other important violations that represent material non-compliance with study drug or protocol that would impact the primary and secondary efficacy endpoints will be reviewed prior to database lock (i.e., before unblinding). These will be documented in the Evaluability Memo which will be included in the clinical study report.

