Subjects in the mITT population who discontinue early from the study, and do not have an assessment of Clinical Cure or Bacteriological Cure will be included in the mITT population as treatment failures. These subjects without actual outcomes, but are classified as treatment failures will not be included in the PP analysis population.

sm **W W I** **W**

Subject demographics and pre-treatment characteristics will be summarized for the ITT analysis population, and some of these summaries may also be done for other populations when deemed important.

sharp

A summary of demographics and subject characteristics will be created for the ITT, Safety, mITT, and PP populations, and include age, race, ethnicity, height, weight, and body mass index (BMI) at the study entry visit with:

- 6-number statistics (number of non-missing observations, mean, median, SD, minimum, and maximum) for age, height, baseline weight, baseline BMI (to be calculated, see formula in [Section 3.8.4](#)) by treatment group and for all subjects.
- Age will be calculated (with the INTCK function in SAS®) using the study entry visit date and the date of birth. Subject age (years) will also be categorized as 18-20, 21-30, 31-40, 41-50, 51+, and then summarized categorically along with race, ethnicity.
- BMI at the study entry visit will also be categorized as: Underweight (< 18.5), Normal (18.5 – 24.9), Overweight (25.0 – 29.9), and Obese (≥ 30.0). The number and percentage of subjects in each of these categories will be presented by treatment group and for all subjects.

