3.7.1 Primary Efficacy Analyses

Primary efficacy endpoint is the “Clinical Cure” at the Test of Cure (TOC) visit (Visit 3) and includes the following 3 parameters from the “Study Procedure” CRF page:

- Resolution of the abnormal vaginal discharge to a normal physiologic discharge, which is from the variable *SPCDBV* (*Was there clinical diagnosis of bacterial vaginosis?*), with value of “No”
- Negative whiff test, which is from the variable *SPWWT* (*Was there a positive whiff test after adding a drop of 10% KOH to vaginal discharge?*), with value of “No”

- Presence of clue cells at < 20% of the total epithelial cells on microscopic examination of the saline wet mount, which is from the variable *SPSWM*, with value of "No".

To investigate therapeutic equivalence, the 90% confidence interval (CI) for difference, [test - reference], in proportion of subjects achieving "Clinical Cure" will be calculated, using the PP analysis population. Adopted from [FDA Office of Generic Drugs Draft Product Specific Guidance for Generic Drug Development on Metronidazole \(Recommended April 2013\)](#) document, the compound hypothesis to be tested here is:

$$H_0: p_T - p_R \leq -0.20 \text{ or } p_T - p_R \geq 0.20$$

versus

$$H_A: -0.20 \leq p_T - p_R \leq 0.20$$

where p_T = cure rate of test treatment and p_R = cure rate of reference treatment.

Let

n_T = sample size of test treatment group

$c n_T$ = number of cured subjects in test treatment group

n_R = sample size of reference treatment group

$c n_R$ = number of cured subjects in reference treatment group

$$P_T = c n_T / n_T, \quad P_R = c n_R / n_R,$$

$$\text{and } \text{se} = (p_T(1 - p_T)/n_T + p_R(1 - p_R)/n_R)^{1/2}$$

The 90% confidence interval for the difference in proportions between test and reference was calculated as follows, using Yates' correction

$$L = (p_T - p_R) - 1.645 \text{ se} - (1/n_T + 1/n_R)/2$$

$$U = (p_T - p_R) + 1.645 \text{ se} + (1/n_T + 1/n_R)/2$$

If the lower limit $L \geq -0.20$ and upper limit $U \leq 0.20$, we will reject null hypothesis H_0 and claim the bioequivalence ("Therapeutic Equivalence") of test treatment GDC-229 and reference treatment.

Two-sided 90% confidence interval (CI), with continuity correction, for the "Clinical Cure" rate of each treatment arm will also be presented, with the following formula:

$$\hat{p} \pm (z_{\alpha/2} \times se(\hat{p}) + (1/2n))$$

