where p is the percentage (proportion) of subjects with “Clinical Cure”, $z_{\alpha/2}$ is the standard normal distribution’s 5th percentile (with $\alpha = 0.1$), and n is the analysis population size in the relevant treatment group, with standard error for the proportion.

$$se(\hat{p}) = \sqrt{\hat{p}(1-\hat{p})/n}$$

PROC FREQ (SAS 9.4) will be employed for the analysis. Proportion of subjects with “Clinical Cure” in test product GDC-229 and reference drug will also be compared against that in placebo group, and p values from chi-square test, or Fisher’s exact test - if any cells have expected frequency of < 5, will be presented. As a parameter for determining adequate study sensitivity, both test product and the reference drug need to have higher “Clinical Cure” rates than placebo and with p values < 0.05, using the mITT analysis population and Last Observation Carried Forward (LOCF), which means if no assessments are available at End of Trial visit (either Visit 3 for completers, or Early Termination (visit 4) for discontinued subjects), then the Visit 2 assessment results will be used. A 95% CI for the “Clinical Cure” rate of each treatment arm will be presented for mITT subjects. The formula for this 95% CI will be the same as above 90% CI except for replacing the α value with 0.05.

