3.7.2 Secondary Efficacy Analyses

The endpoints for secondary efficacy analyses are

- Bacteriological Cure, i.e., Nugent’s score < 4
- Therapeutic Cure, defined as follows:
 - Clinical cure as defined in the Primary Endpoint
 - Vaginal pH < 4.7
 - Nugent’s score < 4 (i.e., Bacteriological Cure)

Total number and proportion of subjects achieving “Bacteriological Cure”, “Therapeutic Cure” (also each of the 3 components) will be presented for mITT population as well as PP population by study visit and treatment arm.

Nugent’s score will also be summarized categorically by its raw score (0, 1, 2, ..., 10). All results from the Amsel’s 4 criteria will also be summarized categorically (“Yes”/ “No”) by study visit and treatment arm for both mITT population and PP population.

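### SAP 3.7.1 carries Visit 2 results forward in the mITT tests against placebo, while SAP 3.4 counts the same early discontinuers as failures, and nothing says which rule prevails

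*SAP*

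**What the plan says.** **Endpoint.** Protocol 9.6.1: "The primary endpoint is the clinical cure at the Test of Cure Visit (Visit 3) and includes the following". SAP 2.4.1 has Clinical Cure "defined as the resolution at the Test of Cure visit", and SAP 3.7.1 places it "at the Test of Cure (TOC) visit (Visit 3) and includes the following 3 parameters". That visit is 21 to 30 days after randomization; Visit 2 is at 7 to 14 days (SAP 2.3).

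**Failure rule.** Protocol 9.2 says that mITT subjects who discontinue early and "do not have an assessment of clinical cure and bacteriological cure will be included in the mITT population analyses as treatment failures". The synopsis says the same. SAP 3.4 repeats the rule with one word changed: such subjects who "do not have an assessment of Clinical Cure or Bacteriological Cure will be included in the mITT population as treatment failures". The protocol joins the two assessments with *and*, the SAP with *or*.

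**Carry-forward rule.** SAP 3.7.1 tests each active arm against placebo in the mITT population with last observation carried forward (LOCF). If nothing is available at the end-of-trial visit, meaning Visit 3 for completers or "Early Termination (visit 4) for discontinued subjects), then the Visit 2 assessment results will be used".

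**Related text.** Gram stain specimens are taken at Visits 1 and 3 (protocol 4.8.4) and at Early Termination, not at Visit 2. Protocol section 9 says deviations from its analysis will be included in the SAP. The only precedence sentence in the SAP, in 3.1.2, lets specific sections override that section's general conventions; it does not rank 3.7.1 against 3.4.

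**The concern.** Take an mITT subject who attends Visit 2 with all three signs resolved, then discontinues without a Visit 3 or Early Termination exam. She has no bacteriological assessment after baseline, so the *or* in SAP 3.4 makes her a failure. SAP 3.7.1 makes her a cure. Two programmers could both follow the SAP and derive different outcomes for her.

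Both active arms must beat placebo in this analysis for the study to show adequate sensitivity, so its outcome rule should be single and fixed before unblinding. LOCF also counts as cured at Test of Cure someone never examined then. If an active effect at Visit 2 fades by Visit 3, that favours the active arms.

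**Working it through.** **1. Side by side, for a discontinuer with a clear Visit 2 exam only**

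| Text | Outcome |
|---|---|
| SAP 3.4 (*or*) | Failure: no bacteriological assessment after baseline |
| Protocol 9.2 and synopsis (*and*) | Failure, if Clinical Cure is assessed only at Visit 3 or if *and* means that lacking either is enough; not reached, if a Visit 2 exam counts and *and* means lacking both |
| SAP 3.7.1 | Cure |

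Protocol 5.2 calls the Visit 2 exam a test of response and reserves clinical cure for Visit 3 (5.3), which favours the first protocol reading without settling it.

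**2. The plan's own figure.** Inputs (protocol 9.1): 36% against 20%, 90% power, 12.4% not in mITT; two-sided 0.05 (protocol 9.6.1).
- Uncorrected: n = [1.960√(2·0.28·0.72) + 1.2816√(0.36·0.64 + 0.20·0.80)]² / 0.16² = 163.4 per arm.
- Continuity-corrected: (163.4/4)·[1 + √(1 + 4/(163.4·0.16))]² = 175.7, so 176.
- 176/0.876 = 200.9, so 201 per arm; × 3 = 603, as stated.

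The stated 90% is therefore a per-comparison figure. Exact power at 176 per arm is 92.1% per comparison and 86.5% for both.

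**3. Effect of the rule (illustrative).** mITT size is 738/3 × 0.876 = 215 per arm. Let m be the share with Visit 2 only, equal across arms and unrelated to outcome; p the Test of Cure rate; v the Visit 2 cure rate. The values of m and v are assumptions.
- Failure rule: rate = (1 − m)p.
- LOCF: rate = (1 − m)p + mv.
- LOCF difference minus failure-rule difference = m × (v active − v placebo).

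Power is by exact binomial enumeration with the uncorrected chi-square test, counting rejections in favour of active. Joint figures are Σ P(x)·s(x)², where x is the placebo count and s(x) the chance that one active arm then wins.

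*Planned rates, 36% against 20%: difference in points, then per-comparison power. With none missing, 16.0 and 96.2%.*

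| m | Failure rule | LOCF, Visit 2 60/25 | LOCF, 50/40 | LOCF, 40/40 |
|---|---|---|---|---|
| 5% | 15.2; 95.0% | 17.0; 97.5% | 15.7; 95.2% | 15.2; 94.0% |
| 10% | 14.4; 93.5% | 17.9; 98.5% | 15.4; 94.1% | 14.4; 91.1% |
| 15% | 13.6; 91.7% | 18.9; 99.1% | 15.1; 92.9% | 13.6; 87.3% |

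*True Test of Cure 25% in all arms: false superiority per comparison (both arms jointly).*

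| m | Failure rule | LOCF, 60/25 | LOCF, 50/40 | LOCF, 40/40 |
|---|---|---|---|---|
| 5% | 2.5% (0.5%) | 6.1% (1.7%) | 3.3% (0.7%) | 2.5% (0.5%) |
| 10% | 2.5% (0.5%) | 12.7% (4.7%) | 4.2% (1.0%) | 2.5% (0.5%) |
| 15% | 2.5% (0.5%) | 22.9% (10.7%) | 5.3% (1.4%) | 2.5% (0.5%) |

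**4. Near the boundary.** 60/215 against 43/215 gives p = 0.055; one more carried-forward cure, 61/215, gives p = 0.043.

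**5. Unequal missingness under the failure rule.** True rate 25% in all arms, 5% missing on active: 0.95 × 25% = 23.75%. Placebo with 10% missing: 22.5%, giving 5.0% false superiority per comparison. Placebo with 15% missing: 21.25%, giving 9.1%.

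**The case against.** **The SAP can be read as LOCF first, failure only if nothing can be carried forward.** SAP 3.7.1 is the only text specific to this test. The failure rule sits under population definitions and would still have work to do: SAP 3.4 requires no post-baseline visit for mITT, and where drug accountability is unknown, as after loss to follow-up, "then subjects will be assumed to have taken study drug and included in the safety population". SAP 3.7.2 presents the cure endpoints and components for both populations: they "will be presented for mITT population as well as PP population by study visit and treatment arm". This is tenable, but the SAP does not say it, and it sets aside the *or* in SAP 3.4.

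**LOCF is not concealed.** A reader might infer an undeclared departure from the protocol. Protocol section 9 asks that deviations be included in the SAP, and LOCF is written there in full. What stands is narrower: it is not flagged as a change or justified.

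**The protocol does not unambiguously make her a failure.** Its *and* can mean lacking both assessments, and Visit 2 checks the same three signs. The firm contradiction is between SAP 3.4 and SAP 3.7.1.

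**The timing argument reaches further than Visit 2.** SAP 3.7.1 also accepts an Early Termination exam, which protocol 5.4 allows at any time. Making only Visit 2 a failure would leave a Day 10 Early Termination exam able to count as a cure. This stands, and the fix must address it.

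**The group may be small.** Sites must make every effort to obtain an early discontinuation exam (protocol 3.4), so 5 to 15% with Visit 2 only may be too high. This also stands.

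**Conclusion.** The point holds as an unresolved conflict between two SAP rules for mITT early discontinuers with Visit 2 only, in the analysis that decides assay sensitivity. On the reading that Clinical Cure is assessed only at Visit 3, LOCF also departs from protocol 9.2 and the synopsis. It should be fixed, but it does not put the primary objective at risk.

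A reader might infer that the equivalence claim is compromised. It is not: the per-protocol population excludes subjects with Visit 3 missing or out of window, except lack-of-efficacy discontinuers with at least 3 doses, who count as failures (SAP 3.4).

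A reader might also take 22.9% as the trial's error rate. The documents do not support that. It is per comparison, and needs 15% with Visit 2 only and a 35-point Visit 2 effect that vanishes by Visit 3. The chance that both arms falsely pass is then 10.7%; at 50/40 it is 0.7 to 1.4% across the range of m, and with equal Visit 2 rates LOCF adds nothing. Nor is the failure rule neutral if missingness differs by arm.

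**What to change.** Before unblinding:
1. In SAP 3.7.1, make the failure rule primary for both superiority tests, so that a subject whose only post-baseline exam is Visit 2 is a failure.
2. Apply it also to subjects who did not discontinue but missed Visit 3. This is an addition; the present wording covers discontinuers only.
3. Align *and* and *or* between protocol 9.2 (with the synopsis) and SAP 3.4.
4. State how Early Termination exams before the Visit 3 window count.
5. Keep LOCF as a labelled sensitivity analysis.
6. Tabulate missing Visit 3 by arm, so that the unequal-missingness risk can be seen.

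The cost is SAP wording and one derivation. Per-comparison power falls from 96.2% to 95.0%, 93.5% and 91.7% at 5%, 10% and 15% missing, and stays at or above the stated 90% up to about 19%. Joint power falls from 93.1% to 91.2%, 88.8% and 85.9%, by the same enumeration. These losses are upper bounds: if the planned 36% and 20% already count missing as failure, there is no loss.

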3.7.2 Secondary Efficacy Analyses

The endpoints for secondary efficacy analyses are

- Bacteriological Cure, i.e., Nugent’s score < 4
- Therapeutic Cure, defined as follows:
 - Clinical cure as defined in the Primary Endpoint
 - Vaginal pH < 4.7
 - Nugent’s score < 4 (i.e., Bacteriological Cure)

Total number and proportion of subjects achieving “Bacteriological Cure”, “Therapeutic Cure” (also each of the 3 components) will be presented for mITT population as well as PP population by study visit and treatment arm.

Nugent’s score will also be summarized categorically by its raw score (0, 1, 2, ..., 10). All results from the Amsel’s 4 criteria will also be summarized categorically (“Yes”/ “No”) by study visit and treatment arm for both mITT population and PP population.

3.7.3 Other Outcome Measurements

The other assessments as follows (each with “Yes”, or “No” answer) on “Study Procedure” form will be presented in data listing:

- Was there a vaginal secretion with pH greater than 4.5?
- Was the saline wet mount assessed for evidence of any other vulvovaginitis other than BV?

- Did the wet mount contain any evidence for candidiasis, Trichomonas vaginalis, Chlamydia trachomatis, Neisseria gonorrhoeae, active herpes simplex, or active HPV?
- Was the urine drug screen performed?
- Were any of the results positive?
- In the last 48 hours have you used any spermicides, tampons, douches, diaphragms, condoms or other intravaginal product?
- Since your last visit have you used any spermicides, tampons, douches, diaphragms, condoms or other intravaginal product?
- Have you had intercourse within the 48 hours prior to a visit?

3.8 Safety Analyses

All safety analyses will be performed for the Safety population unless noted otherwise.

3.8.1 Treatment Exposure and Compliance

Exposure to study treatment will be summarized categorically by

- the number of doses (1, 2, 3, etc.) actually used
- the length of time (# of days) over which the product is used.

The length of time over which the product is used will be calculated as Treatment Stop Date – Treatment Start Date +1.

Treatment Compliance for each subject in Safety population will be calculated as:

$$\text{Number of doses actually used} / 5 \times 100\%,$$

where denominator 5 is the total number of doses supposed to be taken by a randomized subject in this study. The following information for each treatment group will be presented for Treatment Compliance:

- Six-number statistics (sample size, mean, median, SD, minimum, and maximum)
- The number and percentage of subjects in each of the following 4 categories of treatment compliance: <60%, 60% - <100%, 100%, and >100%.

All drug accountability (DA) data on DA form will be presented in a data listing.

3.8.2 Adverse Events and Serious Adverse Events

A treatment-emergent adverse event, (TEAE) is any symptom, sign, illness, or experience that develops or worsens in severity and/or frequency after the study treatment started. A serious adverse event (SAE) is any adverse event that results in any of the following outcomes: Death; immediate threat to life; inpatient hospitalization or prolongation of an existing hospitalization; persistent or significant disability/incapacity; congenital anomaly/birth defect; other serious (medical important) AEs. All AEs will be coded with system organ class (SOC) and preferred term (PT) from the MedDRA Version 20.0. The codings will be reviewed by qualified medical personnel.

Incidence of AEs and SAEs will be summarized by SOC and PT with the number and percentage of subjects with each SOC and PT by treatment arm. The following tables will be presented for Safety population:

- AEs by SOC and PT
- AEs that led to study discontinuation or death by SOC and PT
- AEs by SOC and PT by severity
- AEs by SOC and PT by relatedness to the study treatment
- AEs in descending order of SOC frequencies (no PT displayed)
- AEs in descending order of PT frequencies (no SOC displayed)

All the above tables (except for where specified) are counting number of distinct subjects in each SOC and PT. Subjects reporting more than one AE/SAE in each PT will be counted only once to that PT, using the most severe intensity, for unique number of subjects counting. The only exception to this will be for the summary by relatedness to the study treatment, where subjects will be counted only once using the strongest relatedness to the study treatment for the purpose of counting distinct number of subjects. The same principle also will be applied to the summary at the SOC level.

An overall AE high-level summary table will also be provided for Safety populations with total number and percentage of distinct subjects (but no SOC or PT) for

- AE severity (Mild, Moderate, Severe)
- AE relatedness (Not Related, Possibly Related, Related)
- SAE
- Death, or discontinued study due to any AE

Another high-level summary table for Safety population will present the counts of events (not distinct subjects) as the following chart. Note that each percentage, if provided, is based on the number on the one where "(100.0)" is displayed. This AE summary table, done for each treatment group and all Safety subjects, provides the cross reference between every level of relatedness and severity.

Relatedness (to the study treatment)	AE Severity			Total # (%) of Events
	Mild	Moderate	Severe	
Not Related	xx	xx	xx	xx (x.x)
Possibly Related	xx	xx	xx	xx (x.x)
Related	xx	xx	xx	xx (x.x)
Total # (%) of Events	xx	xx	xx	xx (100.0)

Two listing-style tables, one is for SAEs, and the other is for AEs that led to premature study discontinuation, will also be presented, with the details about the event onset date, resolved date, study day of onset since the study treatment (calculated as Onset Date – Randomization Date +1), severity, outcome, medical intervention needed for the AE, and relatedness to the study treatment, as well as other supportive data such as the subject's age and number of days on the study.

